10 EVALUATIONS BY VISIT

10.1 Visit/Assessment 1: Baseline Survey Assessment (Month 0)

1. Review the study with the participant (participant's legal representative) and obtain written informed consent and HIPAA authorization and assent, if appropriate.
2. Assign the participant a unique screening number.
3. Record demographic data.
4. Record household composition data (number of household members and children).
5. Administer and record current housing situation and history of homelessness instruments, adapted from the Family Options Study and the California Statewide Survey on Homelessness.
6. Administer and record income and employment survey, adapted from the California Statewide Survey on Homelessness.
7. Record concomitant interventions in terms of receipt of assistance from other housing, social, and economic assistance programs.
8. Administer and record monthly expenditure amounts and categories, adapted from the Survey of Income and Participation.
9. Administer and record Financial Well-Being Scale, adapted from the Consumer Financial Protection Bureau (financial well-being).
10. Administer and record Material Hardship Survey, adapted from the Urban Institute Well-Being and Basic Needs and the Survey of Income and Program Participation (material hardship)
11. Administer and record the USDA Brief Food Security Survey (food security)
12. Administer and record healthcare utilization survey, adapted from the California Statewide Survey on Homelessness
13. Administer and record health conditions and functional status survey, adapted from the California Statewide Survey on Homelessness
14. Administer and record Short-Form 12 v2 (physical health)
15. Administer and record Kessler 6 (psychological health)
16. Administer and record the Generalized Self-Efficacy Scale (self-efficacy)
17. Administer and record the Brief Resilience Scale (resilience)
18. Administer and record the Perceived Stress Scale (perceived stress)

19. Administer and record the Confusion, Hubbub and Order Scale (household chaos)
20. Administer and record the Future Scale (aka the Adult Hope Scale) (agency)
21. Schedule participant for Visit 2 in 180-240 days
22. Randomize participant to study group
23. Connect participant with community partner organization (Sacred Heart Community Service) for further social service assessment and assistance (both control and intervention groups) and orientation/navigation for initiation of guaranteed income payments (intervention group)

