14.2 Demographic and Baseline Characteristics

We will summarize the following demographic variables and characteristics at baseline by group assignment: age, gender, race/ethnicity, education, housing status, housing quality/condition, employment, income, financial well-being, material hardship, food security, household composition, health conditions, functional status, healthcare utilization, social service utilization, agency, self-efficacy, perceived stress, household environment.

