14.3 Analysis of Primary Endpoint

We will conduct modified intention-to-treat analyses to assess our primary endpoint, differences in numbers of days spent homeless using Poisson regression.

Analyses will be adjusted for key demographic and clinical characteristics, including: a) referring organization; b) subtype of homelessness; c) preferred payment disbursement schedule (monthly vs hybrid), as well as for covariates that remain unbalanced across the control and intervention groups after randomization. For missing data, we will use multiple imputation, and will employ the last observation carried forward (LOCF), as a sensitivity analysis to assess the robustness of our multiple imputation approach.

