14.6 Sample Size and Randomization

Up to 300 eligible participants will be randomly assigned to the guaranteed income group (intervention) or usual care (control group) using a computer-generated randomization scheme developed by the study team. Eligible participants will be referred by the community partners to the study team for consent and enrollment into the study prior to randomization. Once participants are enrolled, they will be randomly assigned to either the intervention or control group. Group assignments will be known to our community partners, who are administering the guaranteed income intervention; however, the study team (investigators and research staff) will be blinded to group assignments.

For our primary endpoint, number of days experiencing homelessness, given our sample size of 300 with 150 participants in each arm, we estimate that we will have 80% power at a two-sided significance level of 0.05 to detect a mean reduction of 24.0 days in the intervention group, assuming a mean of 52.3 ± 74.0 days experiencing homelessness from prior studies. Allowing for a 27% dropout rate as estimated from prior studies (for a total of sample size of 220 participants with 110 families in each arm), we will still have 80% power at a two-sided significance level of 0.05 to detect a mean reduction of 28.0 days in the intervention group.

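### Homelessness history is collected before randomization but is neither a named covariate in the primary model nor in the baseline list, so the protocol does not secure the precision it could give

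*Protocol*

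**What the plan says.** The primary endpoint is the number of days experiencing homelessness during the study period (Protocol 5.1), analysed by Poisson regression (14.3). The covariates that 14.3 names are "a) referring organization; b) subtype of homelessness; c) preferred payment disbursement schedule (monthly vs hybrid". The list is introduced as key characteristics that include these three, so it is open. Section 14.3 also adjusts for covariates that remain unbalanced between the arms after randomization.

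At the baseline visit, item 5 of section 10.1 reads "Administer and record current housing situation and history of homelessness instruments". Randomization is item 22 of the same visit, section 8.1 confirms that the baseline assessment comes before assignment, and Appendix 1 marks history of homelessness at baseline.

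Section 14.2 lists the characteristics to be summarised by arm. The list begins "age, gender, race/ethnicity, education, housing status, housing quality/condition, employment, income" and continues through financial, health and psychological measures. It has housing status and housing quality, but not homelessness history.

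Section 14.6 claims "80% power at a two-sided significance level of 0.05 to detect a mean reduction of 24.0 days in the intervention group". This is for a "sample size of 300 with 150 participants in each arm", and the outcome distribution behind it is given by the words "assuming a mean of 52.3 ± 74.0 days experiencing homelessness from prior studies".

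**The concern.** The outcome is time spent homeless. Homelessness history is the closest thing to a baseline value of that outcome that the protocol collects, so it is a natural candidate for a prognostic covariate. Adjusting for such a variable improves precision whether or not it happens to be balanced. An imbalance rule is therefore the wrong gate for it: in a well-balanced trial the variable would stay out although it would still help. The gate is also hard to operate here, because an imbalance in a variable missing from the 14.2 list would not show in the listed baseline summary.

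The three named covariates do not clearly fill the gap. Subtype of homelessness describes the kind of homelessness at entry, not how long it has lasted, although the two may be related.

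At stake is the precision of the primary comparison. Against the assumed mean of 52.3 days, the planned detectable reductions are large: 24.0/52.3 = 46% with the full sample and 28.0/52.3 = 54% after dropout. The intervention arm is limited to 150 families by available funds (synopsis), so adjustment is one of the few ways left to gain precision.

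**Working it through.** **Inputs.** From section 14.6: two-sided alpha 0.05, SD 74.0, 150 per arm with 24.0 days. For the second scenario: "Allowing for a 27% dropout rate as estimated from prior studies", leaving "220 participants with 110 families in each arm", with 28.0 days. Not in the documents: rho, the partial correlation between homelessness history and days homeless given the covariates already in the model. I take 0.1 to 0.5 as a range.

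**Step 1: the plan's own figures.** For an unadjusted comparison of two means, SE = SD × √(2/n) and power ≈ Φ(difference/SE − 1.96).

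- 150 per arm: SE = 74.0 × √(2/150) = 8.545; 24.0/8.545 = 2.809; power = Φ(0.849) = 80.2% (79.9% with the noncentral t).
- 110 per arm: SE = 74.0 × √(2/110) = 9.978; 28.0/9.978 = 2.806; power = Φ(0.846) = 80.1% (79.8% with the noncentral t).

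Both statements reproduce, with the full SD and no credit for any covariate.

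**Step 2: adding a baseline covariate.** The residual SD becomes 74.0 × √(1 − rho²). This treats 74.0 as the SD left after the covariates already named, which is a simplification. The detectable reduction at 80% power is (1.96 + 0.842) × SE.

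| Assumed rho | Residual SD | Power, 150/arm, 24.0 days | Power, 110/arm, 28.0 days | Detectable days, 150/arm | Detectable days, 110/arm |
|---|---|---|---|---|---|
| 0 | 74.0 | 80.2% | 80.1% | 23.9 | 28.0 |
| 0.1 | 73.6 | 80.6% | 80.5% | 23.8 | 27.8 |
| 0.2 | 72.5 | 81.8% | 81.7% | 23.5 | 27.4 |
| 0.3 | 70.6 | 83.8% | 83.7% | 22.8 | 26.7 |
| 0.4 | 67.8 | 86.5% | 86.5% | 21.9 | 25.6 |
| 0.5 | 64.1 | 90.0% | 90.0% | 20.7 | 24.2 |

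The gain is under 1 point at rho 0.1, about 4 points at 0.3 and about 10 at 0.5.

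**Step 3: does the gain reach the reported Poisson interval?** Section 14.3 names Poisson regression and does not say how standard errors are obtained. With model-based errors, the SE of the log rate ratio depends only on the total counts. For means of 52.3 and 52.3 − 24.0 = 28.3 at 150 per arm it is √(1/(150 × 52.3) + 1/(150 × 28.3)) = √(1/7845 + 1/4245) = 0.019. Residual variance does not appear in that formula.

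A simulation with these means and a control SD of 74 agrees. The model-based SE stayed at about 0.019 with or without the covariate. The robust SE fell from 0.161 to 0.157 at a correlation of about 0.2, and from 0.159 to about 0.14 at about 0.43. The gain in the reported interval therefore appears only with errors that reflect the real spread of the data.

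**The case against.** The strongest objection is that this is an omission of the kind a SAP settles. Section 14 promises a detailed SAP that may modify the plan, and the wording of 14.3 does not close the covariate list. That stands in part. A reader might infer that the protocol excludes prior homelessness or leaves it no way into the model. The documents do not support this: it could enter through the open list or through the imbalance rule, and neither is limited to the variables in 14.2. What remains is narrower. The protocol chose to name covariates for the primary model, left this one out, and provides an inferior rule for adding others.

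Four further readings go too far.

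- *The trial is underpowered.* It is not, on its own assumptions: the 80% reproduces with no adjustment.
- *All families look alike at baseline because all are homeless.* Section 6.2 admits several situations (the HEARTH definition, hotel or motel, no lease, doubled up), and 14.3 already adjusts for subtype. The correlation that matters is the partial one, which may be small.
- *The interval of the planned model would narrow as soon as the covariate is added.* Step 3 shows that this depends on a variance choice that 14.3 does not state.
- *A continuous count of prior days is already in hand.* The protocol names the instrument but does not show its items, so the form of the variable is unknown.

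**Conclusion.** The point holds as a missed, inexpensive improvement, not as an error in the stated design. Homelessness history is measured before randomization, is a plausible predictor of the outcome, and is fixed neither in the primary model nor in the baseline summary.

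The size is uncertain: negligible if the partial correlation is near 0.1, and worth having from about 0.3 upwards. At rho 0.5, the 110 per arm left after dropout would carry the information of 110/(1 − 0.25) = 147 per arm, close to the 150 enrolled. These figures rest on an assumed correlation and on a comparison-of-means approximation to a Poisson model. They apply to the reported interval only if the standard errors allow for overdispersion.

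**What to change.** 1. In 14.3 (or in the SAP before unblinding), name one measure of prior homelessness from the baseline instrument as a fixed covariate regardless of balance, alongside referring organization and subtype of homelessness. Duration before enrolment is the obvious choice. Use whatever form the instrument yields and state the coding in advance.
2. Specify the baseline administration only. Sections 10.2 to 10.8 list the history instrument again at follow-up, while Appendix 1 marks it at baseline alone; a post-randomization value must not be used as a covariate.
3. State that the Poisson model is reported with robust or dispersion-scaled standard errors.
4. Add the same variable to the 14.2 list.

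The cost is a few sentences and one degree of freedom for a single term. If the instrument does not give a duration, a coarser coding is needed and part of the gain is lost. No extra visit is required and the sample size does not change.

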4 STUDY DESIGN

4.1 Study Overview

This is a single-site, single-blinded randomized controlled trial. The community partner service organizations, Destination: Home SV and the ¡Sí Se Puede! Collective, have raised funds to provide unconditional cash assistance in the form of guaranteed income (GI) for a period of two years to 150 families with children experiencing homelessness in Santa Clara County and who are eligible for referral to rapid rehousing assistance programs (RRH). The partner service organizations are prioritizing assistance to those awaiting RRH referral given the current extended wait time for RRH services. Because there are far more families who are eligible for GI than there are available resources, 150 eligible families will be randomly selected to receive GI. From the pool of eligible families, we will also randomly select an additional 150 participants as matched controls for the purpose of evaluation.

Thus, we are planning for a total of 300 participants. Participants will be assigned to either the control (usual care) or intervention (guaranteed income) groups in random order. Evaluations will be taken at baseline and every 6 months monthly via in-person and/or telephone assessments.

Screening data will be reviewed to determine participant eligibility. Participants who meet all inclusion criteria and none of the exclusion criteria will be entered into the study.

The following treatment regimens will be used:

- Intervention – guaranteed income, consisting of a total of \$24,000 to be disbursed over 24 months. Participants may opt for either monthly (\$1,000/month) or hybrid (lump sum of \$6,500 the first month, then \$500/month x 11 months for a total of \$12,000 per

year) disbursement schedules, with the option to switch disbursement schedule after the first 12 months. Participants will also be invited to attend a Public Benefits Information Session to learn about public benefits and social assistance programs available to residents of Santa Clara County. Participation in this Benefits Information Session will be optional and not required for study participation.

- Control – usual care as per the partner service organizations. Participants will be invited to also attend a Public Benefits Information Session to learn about public benefits and social assistance programs available to residents of Santa Clara County. Participation in this Benefits Information Session will be optional and not required for study participation.

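### The primary model adjusts for a payment-schedule preference that only intervention families are offered, so the term either adds nothing or replaces the randomised comparison

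*Protocol*

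**What the plan says.** Section 14.3 names three adjustment covariates for the primary Poisson model comparing days homeless between arms. The first two are referring organisation and subtype of homelessness. The third is "c) preferred payment disbursement schedule (monthly vs hybrid"). It has two levels, and neither describes a family that receives no payments.

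Section 4.1 describes the choice in the Intervention bullet only: "Participants may opt for either monthly" or hybrid disbursement, "with the option to switch disbursement schedule after the first 12 months". The Control bullet is "usual care as per the partner service organizations", with no payments and no mention of a preference.

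In section 10.1, item 22 is "Randomize participant to study group". Item 23 follows it and includes "orientation/navigation for initiation of guaranteed income payments (intervention group"). Items 1 to 21 contain no schedule preference, nor does Appendix 1. It is also absent from section 14.2, which begins "We will summarize the following demographic variables and characteristics at baseline by group assignment".

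The other mentions are in section 5.2, as topics for semi-structured interviews. There the preferred schedule is one already selected, with a perceived impact. Sections 10.9 and 10.10 place these interviews after randomisation in a subset of 40.

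For incomplete data, section 14.3 states: "For missing data, we will use multiple imputation", with last observation carried forward as a sensitivity analysis.

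**The concern.** A covariate in a randomised comparison should be a baseline characteristic with a value in both arms. Read with sections 4.1 and 10.1, this one exists in one arm only, is settled after allocation, and may change at month 12. The primary result should compare all intervention families with all controls. If the covariate has no control values, the analyst must invent a rule for them, and that rule decides what the arm coefficient means. Two equally natural codings can move the result in opposite directions. Section 8.2 leaves the biostatistician unblinded, which is a further reason not to leave the coding to be chosen later.

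**Working it through.** **The protocol's own figure.** Section 14.6 gives SD 74.0 days, two-sided alpha 0.05, and 80% power for 24.0 days at 150 per arm or 28.0 days at 110 per arm. With SE = 74 × √(2/N) and power = Φ(difference/SE − 1.96):

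- N = 150: SE 8.54, power 80.2%.
- N = 110: SE 9.98, power 80.1%.

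Both stated figures reproduce. They use no covariates.

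**What each handling of controls does.**

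1. *Levels none/monthly/hybrid beside arm.* Arm equals monthly plus hybrid. The columns intercept, arm, monthly, hybrid have rank 3 of 4. Adding referring organisation and an assumed three-level subtype gives rank 6 of 7. The arm coefficient is not separately estimable.
2. *Controls missing and dropped.* No controls remain.
3. *One indicator, 0 in controls.* The arm coefficient compares the intervention families also coded 0 with all controls.
4. *Multiple imputation.* The model can be fitted, but the imputation model rests on no observed control.
5. *Standardising over treated families.* Per simulated trial, this differs from the covariate-adjusted rate ratio without schedule by a median of at most 0.12% (maximum 1.8%).

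**Size under route 3, no true effect.** Let h be the hybrid share and r the ratio of mean days, hybrid to monthly choosers. Both are assumed. With equal overall means in the two arms, the expected arm rate ratio is:

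- hybrid = 1: 1/(1 − h + hr)
- monthly = 1: r/(1 − h + hr)

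For h = 0.5 and r = 1.5 these are 1/1.25 = 0.80 and 1.5/1.25 = 1.20. Simulation agrees. It used 10,000 trials per setting with 150 per arm, negative binomial counts with mean 52.3 and size 0.504 (SD about 74), and Poisson regression on arm and schedule with robust SE. At h = 0.5:

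| r | hybrid = 1: rate ratio (rejection) | monthly = 1: rate ratio (rejection) |
|---|---|---|
| 0.67 | 1.19 (16%) | 0.80 (22%) |
| 1.0 | 0.99 (6%) | 0.99 (6%) |
| 1.5 | 0.79 (22%) | 1.19 (16%) |
| 1.8 | 0.71 (40%) | 1.28 (25%) |

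Over h from 0.3 to 0.7 and these values of r, the hybrid = 1 rate ratio runs from 1.27 to 0.63. Omitting schedule gives 1.00 with 5–6% rejection.

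**With a true effect.** Take the rate ratio (52.3 − 24.0)/52.3 = 28.3/52.3 = 0.541, with h = 0.5 and assumed effects for referring organisation and subtype. Omitting schedule gives 0.540–0.544. The hybrid = 1 indicator gives 0.645, 0.535, 0.431 and 0.386 at r = 0.67, 1.0, 1.5 and 1.8.

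**Multiple imputation.** In the same model (2,000 trials per setting, 10 imputations), the null rate ratio is 0.990–1.003 with 5–7% rejection. The true 0.541 is estimated at 0.543–0.552. The mean SE is 0.0001–0.0008 larger than with the term omitted.

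**Power under route 3 when choice is not prognostic.** With hybrid = 1, only N(1 − h) intervention families inform the coefficient, so SE = 74 × √(1/N + 1/(N(1 − h))). The detectable difference is 2.8016 × SE.

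| h | SE, N = 150 | Power, 24.0 days | Detectable (days) | SE, N = 110 | Power, 28.0 days | Detectable (days) |
|---|---|---|---|---|---|---|
| 0 | 8.54 | 80% | 23.9 | 9.98 | 80% | 28.0 |
| 0.3 | 9.42 | 72% | 26.4 | 11.00 | 72% | 30.8 |
| 0.5 | 10.47 | 63% | 29.3 | 12.22 | 63% | 34.2 |
| 0.7 | 12.58 | 48% | 35.2 | 14.69 | 48% | 41.1 |

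**The case against.** The strongest reply is that section 14.3 says preferred, not received, and lists the item beside two baseline traits. A preference asked of every family before randomisation would be a valid covariate, and the month-12 switch would then be irrelevant. The silence of sections 10.1 and 14.2 and of Appendix 1 proves little, since none of them lists referring organisation either, although it is the stratification factor. Item 23 of section 10.1 does not mention the schedule choice as such. The large numbers all come from one coding that the protocol never states, with assumed shares and ratios. The one rule it does state, multiple imputation, does no harm in these runs. Section 14 also leaves detail to a later SAP.

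Part of this stands. The lists are supporting evidence only, the sizes are assumed, and imputation is harmless. The power table uses the linear scale of section 14.6. On the Poisson scale with robust SE, a smaller set of runs (400 trials, true rate ratio 0.541, non-prognostic choice) had rejection falling from 96% to 88% with half choosing hybrid, so the loss is real but its size depends on the scale.

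The alternative reading, however, has no passage behind it: none says controls are asked, and section 5.2 uses preferred for a schedule already selected. Nor is this detail left to the SAP, because section 14.3 itself fixes the covariate.

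**Conclusion.** The concern holds. As the protocol stands, the third covariate has no observed value in controls, and no way of handling that improves the randomised comparison. Imputation and standardisation give about the result of leaving the term out. A no-payment level or complete-case deletion loses the arm effect. Indicator coding changes what is compared.

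The loss or change of meaning of the arm coefficient does not depend on any assumed number. The size does. Under indicator coding with half choosing hybrid and no true effect, the rate ratio ranges from 0.71 to 1.28 over the ratios examined, and false rejection reaches 40%. There is essentially no bias if choice is unrelated to days homeless, but power on the protocol's own scale still drops to between 72% and 48% for hybrid shares of 30% to 70%. This bears on the primary result and should be corrected before the blind is broken. It is a statistical point and says nothing about which payment schedule is preferable.

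**What to change.** Delete item c from the covariates in section 14.3 and describe payment schedule within the intervention arm only. That costs one clause, keeps the comparison of all intervention families with all controls, and leaves the 80% power calculation unchanged.

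Alternatively, if a preference is or will be elicited from every family before randomisation, say so in section 10.1 and Appendix 1, and have section 14.3 adjust for that baseline value only, not for the schedule later chosen or switched to. That costs one baseline item. It is open only if the answer is recorded before allocation for all families.

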8 STUDY INTERVENTIONS

8.1 Method of Assigning Participants to Treatment Groups

Up to 300 eligible participants will be randomly assigned to the guaranteed income group (intervention) or usual care (control group) using a computer-generated randomization scheme developed by the study team. Eligible participants will be referred by the community partners (DHSV and SSPC) to the study team for consent and enrollment into the study prior to randomization. Once participants are enrolled, they will undergo a baseline assessment before being randomly assigned to either the intervention or control group. Randomization will be stratified by referring community partner (DHSV vs SSPC). Group assignments will be known to our community partners at Sacred Heart Community Service, a neutral third community-based organization contracted by DHSV and SSPC to administer and provide support for the guaranteed income intervention; however, the core study team (investigators and core research staff at UCSF) will be blinded to group assignments.

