14.4 Analysis of Secondary Endpoints

We will conduct intention-to-treat analyses to assess our secondary endpoints, using Cox proportional hazards, logistic and linear regression models as appropriate to the endpoint of interest. Analyses will be adjusted for key demographic and clinical characteristics, as well as for covariates that remain unbalanced across the control and intervention groups after randomization. As sensitivity analyses, we will also conduct per protocol analyses for both our primary and secondary endpoint measures. For missing data, we will employ multiple imputation and use the last observation carried forward (LOCF) as a sensitivity analysis to assess the robustness of the LOCF approach.

For our qualitative assessments, we will use a thematic approach with simultaneous data collection and analysis based on modified grounded theory methodologies. We will review interview transcripts and initial analytic memos to develop a preliminary codebook, code transcripts and iteratively discuss with the study team to add or revise existing codes, have two reviewers independently review transcripts and conduct coding, and hold regular study team meetings to discuss emergent themes until reaching consensus.

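### Sections 14.3 and 14.4 add covariates because the arms happen to differ on them, which leaves part of each model to chance and forgoes the precision of a closed list of prognostic baseline covariates

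*Protocol*

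**What the plan says.** Section 14.3 specifies a modified intention-to-treat analysis of "differences in numbers of days spent homeless using Poisson regression". It adjusts for key characteristics and names three of them: "a) referring organization; b) subtype of homelessness; c) preferred payment disbursement schedule (monthly vs hybrid"). The word that introduces the three makes the list open. The same sentence then adds "covariates that remain unbalanced across the control and intervention groups after randomization".

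Section 14.4 carries the rule to the secondary endpoints, which use Cox, logistic and linear models: "Analyses will be adjusted for key demographic and clinical characteristics, as well as for covariates that remain unbalanced". It names no specific covariate.

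Neither section gives a candidate pool, a measure of imbalance or a cut-off. The nearest thing to a pool is section 14.2, which lists 20 characteristics and says "We will summarize the following demographic variables and characteristics at baseline by group assignment". It mentions no test and is not cited in 14.3 or 14.4.

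The first named covariate is also the stratification factor. Section 8.1 says "Randomization will be stratified by referring community partner (DHSV vs SSPC"). Section 10.1 and Appendix 1 show that homelessness history and the outcome scales are all recorded at baseline. Section 14.6 claims "80% power at a two-sided significance level of 0.05 to detect a mean reduction of 24.0 days in the intervention group" from a comparison of two means with no covariates.

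**The concern.** This is a rule the protocol states, not a detail it leaves to the SAP. An SAP that follows the protocol would inherit it.

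Under correct randomization, whether a baseline variable differs between arms is unrelated to whether it predicts days homeless. Selecting on imbalance therefore brings in variables that may not matter and leaves out prognostic ones that happen to be balanced. A prognostic covariate improves precision whether or not it is balanced, so the rule misses most of the available gain.

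The rule also leaves part of the model unknown until the arms have been compared, under a definition of imbalance that is still to be chosen. Section 8.2 lists the biostatistician among those not blinded to assignment. A closed list removes any question about how that choice was made.

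**Working it through.** **1. The plan's own figures.** Inputs from section 14.6: SD 74.0, two-sided alpha 0.05, power 80%, 150 per arm, or 110 per arm after 27% dropout.

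Detectable difference = (1.960 + 0.842) × 74.0 × √(2/n).

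- n = 150: 23.94 days (stated 24.0). Power for 24.0 days is 80.2%.
- n = 110: 27.95 days (stated 28.0). Power for 28.0 days is 80.1%.
- 300 × (1 − 0.27) = 219 (stated 220).

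The figures reproduce, and they assume no gain from covariates.

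**2. How far chance drives the selection.** The pool and cut-offs here are assumptions, because the protocol gives neither. Take the 20 characteristics in 14.2 and treat them as independent.

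- Tested at 5%: 20 × 0.05 = 1 flagged on average. The chance of at least one is 1 − 0.95²⁰ = 64%.
- Standardized difference above 0.1: each covariate is flagged with probability 2 × [1 − Φ(0.1/√(2/n))], which is 39% at 150 per arm and 46% at 110.
- Standardized difference above 0.2 at 150 per arm: 8%.

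The added set changes greatly with a cut-off that is not stated.

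**3. What fixed adjustment would give.** Residual SD = 74.0 × √(1 − R²). The documents give no R², so a range is shown. The simulated columns come from 4,000 trials per setting, using a linear model, normal outcomes and 20 independent covariates, of which four are prognostic and share the stated R². Four imbalance rules (p<0.05, p<0.10, standardized difference >0.1, >0.2) are compared with always adjusting for the four prognostic covariates. Simulation error (standard error) is about 0.6 points for power, √(0.8 × 0.2/4000), and 0.3 points for type I error, √(0.05 × 0.95/4000).

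| n per arm, effect | R² | Power by formula, fixed | Detectable difference, days | Simulated, imbalance rules | Simulated, fixed | Gap, points |
|---|---|---|---|---|---|---|
| 150, 24.0 d | 0.1 | 84.2% | 22.7 | 79.4–80.0% | 83.4% | 3.4–4.0 |
| 150, 24.0 d | 0.2 | 88.1% | 21.4 | 80.6–82.5% | 87.8% | 5.3–7.2 |
| 150, 24.0 d | 0.3 | 91.9% | 20.0 | 80.0–83.8% | 91.0% | 7.2–11.0 |
| 110, 28.0 d | 0.1 | 84.1% | 26.5 | 79.6–80.4% | 84.5% | 4.1–4.9 |
| 110, 28.0 d | 0.2 | 88.0% | 25.0 | 81.0–82.6% | 88.2% | 5.6–7.2 |
| 110, 28.0 d | 0.3 | 91.8% | 23.4 | 80.0–83.6% | 91.6% | 8.0–11.6 |

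**4. Type I error, same simulation with no effect.** Any one imbalance rule set in advance gives 3.2 to 4.9%. Reporting the most favourable of five options (no added covariates, or any of the four rules) gives 6.2 to 7.9%.

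**5. Limits.** The planned primary model is Poisson, and the planning figures imply a variance-to-mean ratio of 74.0²/52.3 ≈ 105. The simulation is linear and leaves out the three named covariates. It shows direction and rough size only.

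**The case against.** The defence has several good points, and most of them limit the size of the problem.

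- **The primary model is not wholly chosen from the data.** A reader might infer that it is. Section 14.3 names three covariates, including the stratification factor and subtype of homelessness, and whatever precision they bring is kept. Only the addition depends on imbalance. The criticism bears harder on 14.4, where nothing is named.
- **Homelessness history is not excluded.** It is tempting to say that it can enter only if unbalanced. Both sections refer to key characteristics in open terms, and section 14 promises an SAP before the final analysis. What the text supports is that neither section names it.
- **The 64% is illustrative.** Section 14.2 promises summaries, not tests. Its list does not include homelessness history or resilience, although both are recorded at baseline.
- **False positives are not inflated by the rule itself.** A single pre-set rule is slightly conservative. Inflation needs a selective choice among rules, which the protocol does not propose. Baseline balance can be judged without outcomes and no interim analysis is planned, so the unblinded biostatistician is a reason for a closed list and not evidence of bias.
- **The trial is not underpowered by the rule.** The planned 80% assumed no adjustment and is still met.

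None of this supports selecting covariates by imbalance, and leaving the list for the SAP to close does not repair a clause that tells the SAP to reopen it.

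**Conclusion.** The point holds as a flaw in how the adjustment set is defined, and it is worth correcting. It does not invalidate the trial. Part of the primary model and much of each secondary model depend on chance differences and an undefined cut-off.

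The cost is an unrealised gain: about 3 to 11 power points at 150 per arm, or up to about 12 at 110 per arm, for R² between 0.1 and 0.3. That range rests on three things the documents do not settle: the R² itself, a linear model standing in for Poisson, Cox and logistic ones, and covariates that add information beyond those already named. If subtype of homelessness or referring organization already carries much of it, the gain is smaller. How well homelessness history predicts later days homeless, in a cohort that is all homeless at entry, is also an assumption.

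**What to change.** In 14.3 and 14.4, delete the imbalance clause and replace the open wording with a closed list, fixed before any comparison of the arms:

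- all models: referring organization (the stratification factor) and baseline subtype of homelessness;
- housing outcomes, including the primary endpoint: add baseline history or duration of homelessness;
- scale outcomes: add that scale's own baseline value.

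Report observed imbalances descriptively, or explore them in a sensitivity analysis labelled as such.

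Treat preferred payment schedule as a separate, explicit decision. Keep it only if it is recorded before randomization in both arms, which the Visit 1 list in section 10.1 does not show. Removing it would change the stated primary model and should be recorded as a change.

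The cost is protocol and SAP wording. The added covariates are already collected at baseline, so no new data are needed. If anyone has already seen baseline tables by arm when the list is closed, the SAP should say so.
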